8.2.5. Time to Response

The Time to Response will be analysed using comparable methods described in Section 8.2.1. However, the survival function will be plotted based on the complement of the Kaplan-Meier estimates (1-KM) to provide an estimate of the cumulative incidence of response over time.

8.2.6. Clinical Response

Assessment of Clinical Response using the response categories seen in Table 6, will be described using counts and percentages at each visit.

8.2.7. Glucocorticoids Reduction

Number of patients able to reduce glucocorticoids by 50% or more of the baseline dose during emapalumab treatment (Section 6.1.9.4) will be described using counts and percentages.

8.2.8. Number of Patients Proceeding to HSCT

The number of patients proceeding to HSCT (Section 6.1.9.4) will be described using counts and percentages.

[figure not shown]
8.2.9. Quality of Life Assessed Through PedsQL[™], Pediatric Quality of Life Inventory

Descriptive summaries of absolute score and change from baseline will be calculated for the PedsQL total scale score, the health summary scores, and the functioning scale scores (Section 6.1.9.4) for all visits where the questionnaire was completed (Baseline, Visit 3 post-infusion, EOT and follow-up visits D+30, D+100, 6 months and 1 year). PedsQL parent and child/adult reports as well as parent report for infants will be presented separately as outlined in Table 3.

PedsQL subject-data, including derived scores, will be listed.

8.2.10. Quality of Life Assessed Through BASES Questionnaires

The BASES questionnaire scores for the 6 domains (note: activity and sleep subscales will be split into two separate domains due to differing best responses and exploratory nature of questionnaire) at the EOT and follow-up visits D+30, D+100, 6 months and 1 year will be

described using descriptive summaries of absolute values. BASES nurse and parent reports will be presented separately. Only patients with HSCT planned and/or performed will be analysed. Note: HSCT planned is defined as patients captured on the HSCT module of the eCRF with a start of conditioning date or on the CM module with HSCT conditioning medications as indicated in Appendix 15.3.

9. Supplementary Analysis

A supplementary analysis for Overall Response at EOT or Week 8 (whichever occurs earlier) using the definition of Overall Response in Table 7 will be performed. This will be evaluated using an exact binomial test as outlined in Section 8.1 and with the components of the overall response (Complete Response, Partial Response, HLH Improvement and No response) summarized using counts and percentages at Week 8 or EOT (whichever occurs first).

10. Safety and Tolerability Analysis

All safety analyses will be performed as specified in Table 3. All data relating to safety will be listed and summarized using descriptive statistics. No inferential statistical tests will be performed.

The analysis of safety assessments in this study will include summaries of the following categories of safety and tolerability data collected for each patient:

- Adverse events, treatment-emergent AEs (TEAEs), non-TEAEs, serious AEs (SAEs) and non-serious TEAEs
- Clinical laboratory parameters
- Vital signs

Where applicable, analyses will be performed separately for the pre and post-conditioning time periods and by treatment naïve/experienced (unless otherwise specified).

[figure not shown]
Data of patients who have not undergone HSCT will be analyzed in the pre-conditioning period.

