- [†]CBC, coagulation, biochemistry and imaging assessments: If cannot be performed on the day of the scheduled visit, assessments within ±1 day window from scheduled visit date will be accepted.
- ^u Chest X-ray: Chest CT will be accepted as a replacement for Chest X-ray.

Table 2: Schedule of Assessments - Follow-up Period

		Follow-	·up pre-HSCT a		Follow-up post-HSCT (or after last emapalumab infusion, as applicable)					
£	Assessments	EOT ^b	Pre Conditioning visit ^c	Weekly visits wk 1 – 2 – 3 ^d	D+30 visit ^d	D+60 visit ^d	D+100 visit ^d	6 month visit ^d	1 year visit ^d / WD ^e	
	Vital signs		X	X	X	Х	X	Х	X	
	Physical Examination ^g		Х	X	Х	Х	X	X	Х	
	Post-HSCT outcome h			X	X	X	X	X	Х	
Clinical Assessments	QOL - PedsQL [™] , Pediatric Quality of Life Inventory [™]				X		Х	Х	Х	
	QOL – BASES (if HSCT done)				Х		X	Х	Х	
	Survival		X	Х	X	Х	X	Х	Х	
	CBC		X	Х	X	Х	X	X	X	
Labaratanı	Coagulation	As	X	Х	X	Х	Х	X	Х	
Laboratory	Biochemistry	indicated	Х	Х	Х	Х	Х	Х	Х	
	Urinalysis	in Table 1	X	Х	X	Х	X	X	Х	
Search for	TB ^m				Х	Х	Х	Х	Х	
infections	Infection search & monitoring			In cas	e of suspicion of infec	tion - according to t	he patient's clinical pr	esentation		
	Chest X ray i		Χi			In case of su	spicion of infection			
Imaging	Abdominal US ^j		Х				Х		Х	
AE recording ⁿ			Х	Х	X	Х	X	Х	Х	Х
PK/PD (emapalumab concentrations / total IFNy and other biomarkers)			Х	X ^k	Х	Χ¹	Χı	ΧI	Χ¹	
Immunogenici	ty (ADAs)						Х		Х	

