6.3.5 Additional HLH treatments

The administration of additional HLH treatments (e.g., etoposide, T-cell depleting agents) will be allowed concomitantly with emapalumab.

In a patient in whom an HLH worsening or no initial response has been observed after an increase of emapalumab dose to 6 mg/kg on SD3, at SD6 the Investigator may consider the therapeutic option of adding an alternative HLH treatment while continuing emapalumab.

Benefit/risk of administering an additional HLH treatment (with or without emapalumab dose increase) must be assessed, taking into consideration e.g. possible drug toxicities, trends of relevant clinical/laboratory parameters in that individual patient, extent of past response to conventional HLH therapy (if a second-line patient).

The administration of an additional HLH treatment is also allowed later during the course of emapalumab treatment in case of unsatisfactory HLH control, provided that emapalumab has been administered at a dose of 6 (or 10 mg/kg if the Investigator decided to do so) for at least 2 infusions.

Unsatisfactory HLH control is defined as follows:

- patients who have not achieved or maintained a disease control and general conditions that would allow to proceed to transplant
- patients who present a clinically relevant worsening.

If an additional HLH treatment is needed, etoposide is the drug of choice, unless there is evidence indicating that an alternative agent should be selected. The rationale for administration of additional HLH treatments (including the choice of an agent alternative to etoposide, if applicable) has to be documented in the patient's medical file and in the Dose Notification Form (Appendix E).

At any time, the Investigator can decide to discontinue emapalumab treatment and opt for a different HLH regimen in the patient's best interest, as described in the Section 10.1.3.

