The following assessments are to be performed post-infusion at Visit 3 and onwards:

Vital sign assessment:

 Heart rate, oxygen saturation, blood pressure and temperature at the end of the infusion, 1 hour and 2 hours after completion of emapalumab infusion

PK:

 Emapalumab serum concentration (every other infusion starting from Visit 3)

Clinical Assessment:

 QOL questionnaire - PedsQL[™], Pediatric Quality of Life Inventory[™] (at Visit 3 only)

During treatment, emapalumab and biomarker concentrations may be measured in other matrices, such as CSF or BAL, if samples obtained in procedures which are performed for diagnostic/therapeutic purposes can also be available for these exploratory investigations, and if clinically indicated.

8.5 WEEK 8 ASSESSMENT VISIT (3 DAYS AFTER WEEK 8 INFUSION) AND END OF TREATMENT VISIT (3 DAYS AFTER LAST EMAPALUMAB INFUSION)

These visits will include a full patient's assessment.

The Week 8 Assessment Visit will be performed 3 (± 1) days after the last Week 8 emapalumab infusion. If treatment with emapalumab is completed before Week 8, only an EOT visit will be performed 3 (± 1) days after the last infusion.

For patients continuing treatment beyond Week 8, an EOT visit will be conducted 3 (± 1) days after the last emapalumab infusion.

The following assessments are to be performed at the Week 8 Assessment Visit and at the EOT Visit:

Clinical Assessment:

- Vital signs, including body temperature, heart rate, blood pressure, and oxygen saturation
- Physical examination, including as a minimum, weight, spleen and liver size (by abdominal palpation), and neurological examination
- Assessment of clinical response
- QOL questionnaires PedsQL[™], Pediatric Quality of Life Inventory[™],
 BASES (BASES only at EoT and if HSCT is planned)

Procedure:

ECG (only at EOT)

Search for infections:

- TB by PCR (if not performed within the last 4 weeks)
- Infection search & monitoring in case of suspicion of infection or if there is an active infection at screening/baseline to monitor evolution of viral load and positivity for an identified pathogenAtypical mycobacteria, Histoplasma Capsulatum, Shigella, Salmonella, Campylobacter, Leishmania – only if an infection is suspected

Study NI-0501-09 NI-0501 in Primary HLH Page 54 of 92

Laboratory:

 CBC with differential count (including large unstained cells count, whenever performed as routine)

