TEAE with infusion-related reactions (IRRs)	Any AE reported to have occurred within 24 hours after the start of infusion and reported as related to study treatment by the Investigator, excluding the following SOCs: "Infections and infestations," "Congenital familial and genetic disorders," "Neoplasms benign, malignant and unspecified (incl. cysts and polyps)," "Product issues," "Social circumstances," and "Surgical and medical procedures."			
	If the onset time of the AE or the start time of the infusion is missing, then an AE with an onset date equal to an infusion date or infusion date +1 will be considered for the assessment of IRRs, unless the available information clearly indicates the AE was not treatment-emergent.			

*Note: The start date of conditioning is captured in the HSCT module of the eCRF or CM module. For more information of HSCT medications see Appendix 16.2.

AD-ST-33.06 Effective date: 12-Nov-2020

[figure not shown]

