16.2. Concomitant Medications for HSCT Conditioning

Table 19: Concomitant HSCT Conditioning Medication Preferred Terms

ATC Level 4	Preferred Code	Preferred Text
L01AA	00021101001	CYCLOPHOSPHAMIDE
201121	00006401001	MELPHALAN
L01AB	00036801001	BUSULFAN
	00418901001	TREOSULFAN
L01AC	00053501001	ТНІОТЕРА
L01BB	02122001001	CLOFARABINE
LUIDD	01004601001	FLUDARABINE
	01004602001	FLUDARABINE PHOSPHATE
L01BC	00146201001	CYTARABINE
L01BC	00511901001	ETOPOSIDE
20120	00511902001	ETOPOSIDE PHOSPHATE
L01XC	01402501001	RITUXIMAB
L04AA	01268601001	ALEMTUZUMAB
Lonni	00575401001	ANTITHYMOCYTE IMMUNOGLOBULIN
	00575402001	ANTITHYMOCYTE IMMUNOGLOBULIN (RABBIT)
	02082701001	ANTILYMPHOCYTE IMMUNOGLOBULIN

16.3. Disease Indicating Central Nervous System (CNS) Involvement / CSF abnormalities by Medical History/AE Preferred Term and Code

[figure not shown]
Preferred Term Code	Preferred Term
10029818	Nuclear magnetic resonance imaging brain abnormal
10059703	CSF test abnormal
10053805	CSF white blood cell count increased
10011522	CSF cell count increased
10035551	Pleocytosis
10012559	Developmental delay
10056832	Neurological examination abnormal
10047641	VIth nerve paralysis
10020745	Hyperreflexia
10041962	Status epilepticus
10039906	Seizure
10021118	Hypotonia
10002948	Aphasia
10029202	Nervous system disorder
10017577	Gait disturbance
10048334	Mobility decreased
10008096	Cerebral atrophy
10015037	Epilepsy
10071066	Posterior reversible encephalopathy syndrome
10022840	Intraventricular haemorrhage

The overall response criterion 'No neurological and CSF abnormalities attributed to HLH' is not fulfilled during the time period in which any of the above listed AEs is present or the assessment on neurological examination CRF is 'abnormal' with comment 'CNS involvement'.

AD-ST-33.06 Effective date: 12-Nov-2020

Statistical Analysis Plan, Sponsor Sobi AG

Protocol Number NI-0501-09 PCN Number 176784

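### SAP 8.2.10 limits the end-of-treatment BASES summary to patients with transplant planned, but identifies them by conditioning records and not by the plan at that visit

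*SAP*

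**What the plan says.** **Collection.** Protocol Section 8.5 asks for "BASES only at EoT and if HSCT is planned", and a footnote to the schedule of assessments (Table 1) says the same. From Day 30 onward, Table 2 and Sections 8.6.2 and 8.6.3 collect BASES only where the transplant has taken place. The word *planned* therefore matters for one visit only, EOT.

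**Analysis.** SAP Section 8.2.10 states: "Only patients with HSCT planned and/or performed will be analysed". Its note then says that "HSCT planned is defined as patients captured on the HSCT module of the eCRF with a start of conditioning date", and the sentence continues "or on the CM module with HSCT conditioning medications as indicated in Appendix 15.3".

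**What the two routes stand for.** The footnote to SAP Table 5 (Section 6.1.9.3) says: "The start date of conditioning is captured in the HSCT module of the eCRF or CM module". It points to Appendix 16.2 for the drugs, where Table 19 ("Concomitant HSCT Conditioning Medication Preferred Terms") includes etoposide, alemtuzumab, antithymocyte immunoglobulin (ATG) and rituximab.

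**Other uses of those drugs.** On additional HLH treatment, Protocol Section 6.3.5 says: "If an additional HLH treatment is needed, etoposide is the drug of choice", with an exception where evidence favours another agent. The same section allows T-cell depleting agents, and Section 6.3.4 allows rituximab for documented EBV infection.

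**The concern.** The protocol asks a question about intent at EOT: is a transplant planned? The SAP answers it with records showing whether conditioning took place. A patient can complete the form because a transplant is intended and then never reach conditioning. If the analysis set depends on reaching it, a summary labelled as EOT describes only those who got further.

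The gap is possible under this design. EOT and pre-conditioning are separate visits, combined only when they are no more than 2 days apart. Treatment may not exceed 6 months and may be stopped at any time, and the protocol foresees lack of a donor. Survival to HSCT and the number proceeding to HSCT are both secondary endpoints, so the plan itself expects some patients not to get there.

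At stake is whether Tables 14.2.10.1 and 14.2.10.2 describe, at EOT, the population in which the protocol collected the form.

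**Working it through.** The documents give no count of patients planned for HSCT, patients conditioned, or EOT BASES forms. There is thus no figure to reproduce, and the check is a comparison of definitions.

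**Step 1: both routes point to conditioning.** Route 1 is a conditioning start date in the HSCT module. Route 2 is a listed drug in the CM module, which Section 6.1.9.3 treats as a second source for the same date. Neither document names an eCRF field or rule for a transplant that was planned but not started.

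**Step 2: apply the definitions to each type of patient.** The last column assumes no HSCT was performed unless conditioning started.

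| Patient | EOT BASES due under protocol | In SAP summary |
|---|---|---|
| Planned at EOT, conditioning started | Yes | Yes |
| Planned at EOT, never conditioned, no Table 19 drug in CM | Yes | No |
| Planned at EOT, never conditioned, Table 19 drug given for HLH or EBV | Yes | Yes if read literally; no if read as in Section 6.1.9.3 |
| Died before any EOT visit | No form exists | Nothing to lose |
| HSCT not planned, Table 19 drug given for HLH or EBV | No | Classed as planned if read literally |

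Row 2 is the loss. Row 3 is ambiguous. Row 5 is the opposite error; since no form is due there, it affects the label and any denominator more than the scores.

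**Step 3: the cross-reference.** SAP Section 15 has only 15.1 and 15.2, so Appendix 15.3 does not exist. Tables 6 and 7 cite the same number for the CNS and CSF terms, which are in Appendix 16.3. Renumbering 15 to 16 would therefore lead to the wrong list; the conditioning drugs are in Appendix 16.2.

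**Step 4: comparison within the SAP.** Section 8.2.9 summarises PedsQL at every visit where a form was completed, with no condition on later events. Section 11, which lists changes from the protocol, does not mention the narrower meaning of *planned*.

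**Step 5: scale, by assumption only.** If the row 2 group were 5% to 30% of the 34 treated patients, then 34 × 0.05 = 1.7 and 34 × 0.30 = 10.2, or about 2 to 10 patients. With the maximum of 41, 41 × 0.05 = 2.1 and 41 × 0.30 = 12.3, or about 2 to 12. Nothing in the documents supports any particular share; this is a scale and not an estimate.

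**The case against.** The best defence is that BASES is of interest because it focuses on transplant, has no baseline assessment, and is collected after EOT only in transplanted patients. Following one conditioned or transplanted cohort from EOT through follow-up is a coherent choice, and the fault may then be only the label. That is fair for a longitudinal description. It does not justify calling the group *planned* at EOT, or leaving unstated how many completed forms fall outside it.

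The affected group is also narrow. Treatment is meant to run until conditioning, with no wash-out, and the EOT visit is 3 ± 1 days after the last infusion. Many patients who worsen will still be on treatment and will not have had an EOT visit. This stands.

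A reader might infer more than the documents support:

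- *That all planned patients who die or worsen before conditioning are removed.* Those who die before EOT have no form, and the CM route, read literally, keeps those given a Table 19 drug.
- *That the forms are lost.* They remain in Listings 16.2.6.10 and 16.2.6.11, which cover the All Treated population.
- *That the scores must look too good.* This is plausible but not shown. The study enrols suspected cases, and the Evaluable Analysis Set definition anticipates a later diagnosis of secondary HLH, so a transplant plan could lapse without deterioration.
- *That a shift in an EOT mean can be stated.* The SAP reports six domains, with parent and nurse forms separate and the best score at opposite ends for different domains. The documents give no input for such a shift.

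**Conclusion.** The point holds as a mismatch of definitions. The protocol collects EOT BASES on intent, while the SAP selects on conditioning, which follows EOT, through a drug route loose enough to misclassify in both directions. Patients with a completed EOT form, no conditioning and no Table 19 drug are left out of the EOT tables.

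The number affected and the direction of any bias cannot be obtained from the documents. The effect of the CM route also depends on whether it is read literally or as a source for the conditioning date.

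The impact is low. The form is a reduced, non-validated 22-item version, used in an exploratory way and summarised descriptively. P-values are confined to Overall Response, so no primary or safety conclusion depends on this. It is worth correcting because BASES is a listed secondary endpoint and the correction is simple.

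**What to change.** In SAP Section 8.2.10, before database lock:

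1. Summarise EOT BASES in all patients with a completed EOT form, following the approach of Section 8.2.9 for PedsQL.
2. Use the transplanted group for the Day 30, Day 100, 6-month and 1-year visits.
3. Wherever the CM route is kept, limit it to drugs given as conditioning, by date or indication. Section 10.9 already separates concomitant medication for HLH from other medication, so a split by indication is foreseen.
4. Change the reference from Appendix 15.3 to Appendix 16.2.
5. Report how many patients with an EOT form never started conditioning. If the sponsor also wants a single cohort across visits, show it as a second, clearly labelled summary.

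The cost is SAP wording and minor table programming. No new data are needed.

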6.1.9.3. Safety Parameters

Table 4: Definition of Drug Administration Variables

Statistics for Exposure (dosing)	Derivation
Duration of exposure (days)	Date of last infusion of emapalumab – date of first infusion of emapalumab + 1
Duration of exposure (weeks)	Duration of exposure (days)/7
Maximum dose prescribed	Maximum of all doses prescribed (mg/kg)
Cumulative dose (mg/kg)	Sum of total actual dose per kg administered from first infusion date until last infusion date
Average dose frequency (days)	Duration of exposure (days)/ total number of infusions
Average dose of emapalumab per day (mg/kg)	Cumulative dose (mg/kg)/ duration of exposure (days)
Percentage of dose increases from baseline dose	(Number of dose increases from baseline dose / number of total doses) multiplied by 100.
Percentage of dose decreases from baseline dose	(Number of dose decreases from baseline dose / number of total doses) multiplied by 100.

Table 5: Definition of Adverse Events

Variable	Definition
Adverse Event (AE)	All recorded AEs (collection of AEs starts after ICF signature).
Treatment-Emergent Adverse Event (TEAE)	Any AE (serious and non-serious) with an onset date after the start of the first emapalumab infusion.
Pre-conditioning AE	Any AE (serious and non-serious) with start date before the start of conditioning for HSCT*.

[figure not shown]

Variable	Definition			
Post-conditioning AE	Any AE (serious and non-serious) with start date after the start of conditioning for HSCT*.			
TEAEs related to the study drug	Any AEs with an onset date after the start of the first emapalumab infusion with "Relationship to Study Drug" of "Related".			
Serious TEAEs	Any AEs with an onset date after the start of the first emapalumab infusion with "Serious" of "Yes".			
TEAEs leading to withdrawal of study drug	Any AEs with an onset date after the start of the first emapalumab infusion with "Action taken with study drug" of "Drug Withdrawn".			
TEAEs resulting in death	Any AEs with an onset date after the start of the first emapalumab infusion with "Results in death" of "Yes".			
TEAE with infections	Any AE with an onset date after the start of the first emapalumab infusion with system organ class (SOC) 'Infections and Infestations' or in the HLGT 'Microbiology and serology investigations'.			

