- BSA Surface Area (BSA) [VS]
- Equivalent dose $(mg/m^2/day) = Daily dose / BSA$

Glucocorticoid tapering

For the reduction of glucocorticoid dose by 50% or more of baseline dose, the use of glucocorticoid for systemic use during the study period will be obtained by the CM (ATC04ID H02AB) or medications captured on the SSA module of the eCRF. Drug names on the SSA page are standardized (Dexamethasone, Hydrocortisone, Methylprednisolone, Prednisolone, Prednisolone, not coded. The calculation of reduction of glucocorticoid dose by 50% or more of baseline dose will take into consideration the following:

- Dexamethasone (H02AB PREFERRED CODE 00016001001) dose expressed as mg/m2/day at
 - \circ Baseline = SD-1 or closest day to SD0
 - The lowest dose received during the study and the corresponding SD,
 - The dose received at EOT

provided that:

[figure not shown]
- No other glucocorticoids have been received by oral or IV route on the SD of interest with reference to:
 - Methylprednisolone (CM page: H02AB PREFERRED CODE 00049601001)
 - Prednisolone (CM page: H02AB PREFERRED CODE 00016201001)
 - Prednisone (CM page: H02AB PREFERRED CODE 00044701001)
 - Hydrocortisone (CM page: H02AB PREFERRED CODE 00028601001, 00028603001,00028602001)
 - Triamcinolone (CM page: H02AB PREFERRED CODE 00031901001 if single ingredient medication; in case of multiple ingredients medications or salt derivates every entry need to be checked manually for Triamcinolone)
 - Cortisone (CM page: H02AB PREFERRED CODE 00014601001 if single ingredient medication; in case of multiple ingredients medications or salt derivates every entry need to be checked manually for Cortisone)

In that case, the dose of the other glucocorticoids has to be summed up, taking into consideration glucocorticoid conversion.

• Glucocorticoids reduction until EOT

A patient will achieve a glucocorticoids reduction by 50% or more of the baseline dose if the equivalent dose of dexamethasone at any post-baseline time until EOT is less than or equal to (\leq) ¹/₂ the equivalent dose of dexamethasone at baseline. This reduction has to be maintained for at least one week.

• Patients proceeding to HSCT = patient with HSCT (date of HSCT non missing in the HSCT module of the eCRF).

Quality of Life Parameters

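### SAP Section 10 assigns safety data to the pre-conditioning period by whether HSCT took place, while Table 5 uses the start of conditioning, so patients conditioned but never transplanted are classified in opposite ways

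*SAP*

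**What the plan says.** SAP Section 6.1.9.3, Table 5, defines a pre-conditioning AE as "Any AE (serious and non-serious) with start date before the start of conditioning for HSCT" and a post-conditioning AE as "Any AE (serious and non-serious) with start date after the start of conditioning for HSCT". The footnote gives the source of the cut-point: "The start date of conditioning is captured in the HSCT module of the eCRF or CM module". Section 10.1 points back to Table 5 for its AE definitions.

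Section 10, just before Section 10.1, says that safety analyses are done separately for the two periods where applicable, and then adds: "Data of patients who have not undergone HSCT will be analyzed in the pre-conditioning period". It makes no exception for patients who had started conditioning.

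Elsewhere the SAP keeps the two states apart. In Section 6.1.9.4 a patient counts as having proceeded to HSCT only if an HSCT date is recorded. In Section 8.2.10, by contrast, "HSCT planned is defined as patients captured on the HSCT module of the eCRF with a start of conditioning date"; conditioning medication recorded on the CM module also qualifies. In the list of planned tables (Section 14.1), the post-conditioning infection table, 14.3.2.5.2, is restricted to patients who have a conditioning start date, whether or not a transplant followed.

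**The concern.** Two different events serve as the dividing line for the same outputs. For most patients this makes no difference: someone never conditioned has only pre-conditioning data under either rule, and someone conditioned and transplanted is split by Table 5. The rules part only for a patient who begins conditioning and then dies, deteriorates or loses the donor before the graft.

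For that patient, toxicity of the conditioning regimen can be tabulated as pre-conditioning. The study has a single arm, so no control group helps separate the effects of emapalumab from those of conditioning, and the period split is one of the few descriptive tools for doing so. Protocol Section 9.2.1 exempts expected conditioning effects, given as pancytopenia until engraftment, from AE reporting. Other conditioning toxicities do enter the AE data.

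**Working it through.** The plan gives no figure to reproduce, and the point rests on no sample size or event rate. The check is to apply both written rules to the same AE, taking the day conditioning starts as day 0.

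**Rule A (Table 5):** pre-conditioning if the AE starts before day 0; post-conditioning if it starts after.

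**Rule B (Section 10):** pre-conditioning if the patient did not undergo HSCT.

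| Patient | AE start day | Rule A | Rule B | Result |
|---|---|---|---|---|
| Conditioned, no HSCT | -1 | pre | pre | agree |
| Conditioned, no HSCT | 0 | not stated literally | pre | tie not settled by A |
| Conditioned, no HSCT | +1 | post | pre | conflict |
| Conditioned, no HSCT | +5 | post | pre | conflict |
| Conditioned, HSCT done | -1 | pre | does not apply | pre |
| Conditioned, HSCT done | 0 | not stated literally | does not apply | tie not settled by A |
| Conditioned, HSCT done | +1 or +5 | post | does not apply | post |

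So every AE starting after day 0 in a conditioned, non-transplanted patient is classified in opposite ways.

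**Outputs affected (Section 14.1):** the overview tables before and after conditioning (14.3.1.1.2 and 14.3.1.1.3), the TEAE tables by period (14.3.1.5.1 to 14.3.1.5.3 and 14.3.1.6.1 to 14.3.1.6.3), serious TEAEs by period (14.3.2.3.2 and 14.3.2.3.3) and infections by period (14.3.2.5.1 and 14.3.2.5.2). Listings 16.2.7.1.2 and 16.2.7.1.3 carry the same split. The infection tables show the inconsistency directly: such a patient belongs to the population of 14.3.2.5.2, while Section 10 sends the same patient's infections to 14.3.2.5.1.

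**Outputs not affected:** the unsplit AE and TEAE tables (14.3.1.1.1, and 14.3.1.2.1 to 14.3.1.4.3), serious TEAEs overall (14.3.2.3.1), fatal TEAEs (14.3.2.2) and all efficacy results.

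**The conditioning day.** Table 5 gives no tie rule, but the SAP's use of parallel wording suggests one. Table 5 also defines a TEAE as starting after the start of the first infusion. Section 6.1.10 nevertheless imputes a wholly missing onset date to the first-infusion date and counts that AE as treatment-emergent, unless its end date shows otherwise. By analogy, an AE on the conditioning day is post-conditioning.

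**The case against.** The best defence is that Section 10 states a default for patients who have no cut-point, and that Table 5, as the more specific rule, governs everyone else. The SAP does use lack of HSCT as shorthand for lack of conditioning elsewhere: in Section 6.1.9.4, cumulative duration of response runs to conditioning, or to end of treatment if HSCT was not performed. The population of Table 14.3.2.5.2 also suggests that Table 5 is meant to prevail. This is probably the intention, but Section 10 does not say so. The SAP recognises conditioning without transplant as a separate state, so a programmer following the sentence as written would misplace those events.

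The defence is right on consequence. A reader might infer that conditioning toxicity would be presented as on-drug toxicity. The documents do not support that: the pre-conditioning period is not an on-treatment period, because never-transplanted patients are followed for one year after the last infusion and their data sit there by design. TEAEs in each period are also tabulated by relationship to study drug, so attribution does not rest on the split alone.

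A reader might also infer that deaths would be misreported. The dedicated fatal-TEAE table is not split by period. At most, a fatal event could sit in the wrong period overview if those tables carry the row for TEAEs resulting in death that Section 10.1 lists. The table shells are a separate document and cannot be checked here; they might also contain a programming note that resolves the matter.

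**Conclusion.** The inconsistency stands on the text and is minor. It concerns only patients who start conditioning and are never transplanted, and only the period-split safety outputs. All safety analysis is descriptive, so no test is affected.

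No size can be given. The documents contain neither a count of such patients nor a rate of their AEs, and the true number may be zero. Any percentage would rest on an invented event count.

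A reader might also conclude from Table 5 that AEs starting on the conditioning day fall out of the analysis. That goes too far. The SAP's handling of the first-infusion day points to counting them as post-conditioning, and they remain in all the overall tables and the full AE listing in any case. What is missing is an explicit statement.

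The conclusion assumes that the Section 10 sentence applies as written and that no rule in the separate shells overrides it.

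**What to change.** In SAP Section 10, change the condition from not having undergone HSCT to not having started conditioning. The sentence then covers only patients without a cut-point, and Table 5 governs all conditioned patients, transplanted or not, in line with Table 14.3.2.5.2.

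As a minor clarification, state in Table 5 that a post-conditioning AE is one starting on or after the date conditioning starts.

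The cost is one changed phrase and one clarifying phrase. The conditioning start date is already collected, so no new data or tables are needed. Making the change before database lock avoids deciding where serious events belong after they have been seen.
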